8.2 Missing or Inconclusive Data Handling

| Term | Percentage |
|------------|------------|
| GMOs | 85 |
| Organic | 92 |
| Natural | 90 |
| Artificial | 65 |
| Organic | 88 |
| Natural | 85 |
| Artificial | 68 |
| Organic | 89 |
| Natural | 87 |
| Artificial | 70 |
| Organic | 91 |
| Natural | 89 |
| Artificial | 72 |
| Organic | 93 |
| Natural | 91 |
| Artificial | 74 |
| Organic | 94 |
| Natural | 92 |
| Artificial | 76 |
| Organic | 95 |
| Natural | 93 |
| Artificial | 78 |
| Organic | 96 |
| Natural | 94 |
| Artificial | 80 |
| Organic | 97 |
| Natural | 95 |
| Artificial | 82 |
| Organic | 98 |
| Natural | 96 |
| Artificial | 84 |
| Organic | 99 |
| Natural | 97 |
| Artificial | 86 |
| Organic | 100 |
| Natural | 98 |
| Artificial | 88 |

The image consists of a high-contrast, black-and-white pattern. It features a large, dark, irregular shape in the center, which appears to be a redacted area. This central shape is surrounded by a series of horizontal and vertical black bars of varying lengths. The overall effect is reminiscent of a heavily processed or redacted document page.

A high-contrast, black and white image showing a complex, abstract pattern of horizontal and vertical bars. The pattern is composed of various lengths of black lines on a white background, creating a stepped, architectural appearance. The image is heavily processed, appearing as a binary black and white graphic.

8.3 Definition of Baseline

For the primary efficacy variables (ocular itching and conjunctival redness), baseline will refer to the time point specific measure at Visit 3 (e.g., ocular itching at 5 minutes post-CAC at Visit 3 will be the baseline for ocular itching at 5 minutes post-CAC at Visits 4b, 5a, 5b, 6a, 6b, and 7).

Baseline for all secondary efficacy variables is defined in a manner similar to the baseline for the primary efficacy variables. For all safety variables, baseline is defined as the last measurement prior to the first dose of study medication.

8.4 Data Analysis Conventions

All data analysis will be performed by SDC. Statistical programming and analyses will be performed using SAS® Version 9.4 or higher. Output will be provided in rich text format (RTF) for tables and portable document format (PDF) for tables, listings, and figures using landscape orientation. All study data will be listed by subject, treatment, and visit/time point (as applicable) based on all randomized subjects unless otherwise specified.

Summaries for continuous and ordinal variables will include the number of observations (n), arithmetic mean, SD, median, minimum, and maximum. Minima and maxima will be reported with the same precision as the raw values; means and medians will be presented to one additional decimal place than

reported in the raw values. Standard deviations will be presented to two additional decimal places than reported in the raw values. Summaries for discrete variables will include frequency counts and percentages. All percentages will be rounded to one decimal place (i.e., XX.X%). Differences between active treatment groups and vehicle or active control will be calculated as active minus vehicle or active control and change from baseline will be calculated as follow-up visit minus baseline.

All statistical tests will be two-sided with a significance level of 0.05 ($\alpha = 0.05$) unless otherwise specified. Confidence intervals (CI) for differences between treatment groups will be two-sided at 95% confidence. All p-values will be rounded to four decimal places; p-values less than 0.0001 will be presented as "<0.0001"; p-values greater than 0.9999 will be presented as ">0.9999".

Unless otherwise specified, summaries will be presented by treatment group and, where appropriate, visit/time point.

8.5 Adjustments for Multiplicity

There will be no adjustment for multiplicity for having two endpoints as statistical significance is required for both ocular itching and conjunctival redness for treatment success. There will also be no adjustment necessary for testing multiple time points within a given visit, as significance at all post-CAC time points is required.

Since this is a proof of concept study, there will be no adjustment for multiplicity of testing two concentrations of PRT-2761 versus placebo.

9. Disposition of Subjects

Subject disposition will be presented in terms of the numbers and percentages of subjects who were randomized, completed the study, and discontinued from the study. Subjects who are not discontinued from the study will be considered study completers. Disposition will be summarized by treatment group and for all subjects.

The number and percentage of subjects prematurely discontinued from the study and the reasons for study discontinuation will be summarized by treatment group for all randomized subjects. The reasons for study discontinuation that will be summarized include: AE, protocol deviation, administrative reasons, manifest signs of allergic conjunctivitis at Visit 5a, sponsor termination of study and other. A subject listing will be provided that includes the date of and reason for premature study discontinuation.

Subject listings will be provided that include informed consent date, inclusion and exclusion criteria, deviations, and exclusions from the PP population.

Protocol deviations will be summarized by treatment group for all randomized subjects for each deviation category (informed consent, inclusion/exclusion and randomization, test article/study drug instillation and assignment at site, improper protocol procedures at site, site failure to report SAE, visit out of

window [missed, early, late], subject's non-compliance with test article/study drug, subject use of prohibited concomitant medication, subject's failure to follow instructions, other) and severity (minor, major) using counts and percentages. Percentages will be based on the total number of subjects randomized in each treatment group. A subject listing will be provided that includes the date of the deviation, the deviation description, and the classification of whether the deviation was judged to be major or minor.

10. Demographic and Pretreatment Variables

10.1 Demographic Variables

The demographic variables collected in this study include age, gender, race, ethnicity, and iris color. Subjects who record more than one race will be grouped into a single category denoted as multi-racial. Demographic variables will be summarized for the ITT and Safety populations, separately.

Age (years) will be summarized, overall and by treatment, using continuous descriptive statistics. Age will also be categorized as follows: <65 years and ≥65 years. Age will be reported in years and calculated using the following formula:

$$\text{Age} = (\text{informed consent date} - \text{date of birth}) / 365.25 \text{ truncated as an integer}$$

The number and percentage of subjects will be presented, overall and by treatment, for age category, sex, race, ethnicity, iris color, average post-CAC itching scores at baseline [REDACTED] allergen type, and confocal participation.

A subject listing that includes all demographic variables will be provided.

10.2 Pretreatment Variables

At Visit 1 (Day -50 to -22), subjects signing the informed consent and Health Insurance Portability and Accountability Act (HIPAA) forms may be given a diagnostic test for allergic disease (skin test). Results from this test will be provided in a subject listing.

11. Medical History and Concomitant Medications

11.1 Medical History

Medical history will be coded using Medical Dictionary for Regulatory Activities (MedDRA) Version 20.1.

Non-ocular medical history will be summarized using discrete summary statistics and presented by treatment group at the subject level by System Organ Class (SOC) and Preferred Term (PT) using the ITT population. Ocular medical history will be similarly summarized at the subject level. If a subject reports the same PT multiple times within the same SOC, that PT will only be reported once within that SOC. As with the PT, if a subject reports multiple conditions within the same SOC, that SOC will only be reported once.

Listings of medical history will be generated separately for ocular and non-ocular data.

11.2 Concomitant Medications

The use of any concurrent medication, prescription or over-the-counter, is to be recorded on the subject's source document and corresponding eCRF along with the reason the medication was taken.

Concomitant medications will be coded using the World Health Organization Drug Dictionary (WHO DD, Enhanced B2, September 2017) and summarized to the therapeutic drug class (Anatomical Therapeutic Chemical [ATC] 4 classification) and preferred name. If the ATC 4 classification is not provided, the next lowest classification that is provided in the coding dictionary will be used. The preferred name will be defined as the active ingredient; if the active ingredient is not provided or includes more than two ingredients (e.g., multivitamins) then the drug name will be summarized as the preferred name.

Concomitant medications will be summarized using the ITT population. Medications will be tabulated for each treatment group using frequencies and percentages. Subjects may have more than one medication per ATC text. At each level of subject summarization, a subject will be counted once if he/she reports one or more medications. Percentages will be based on the number of randomized subjects in each treatment group. Listings of concomitant medications will be generated separately for ocular and non-ocular data.

12. Exposure to Investigational Product

The number and percentage of subjects instilled with IP will be summarized by visit and treatment group for the Safety population. Percentages will be calculated based on the total number of subjects in each treatment group with responses.

A listing of IP instillation for all subjects will also be provided.

13. Efficacy Analyses

13.1 Primary Analysis

The primary efficacy endpoints are ocular itching assessed by the subject at 5(± 1), 7(± 1), 10(± 1) minutes post-CAC (0-4 scale, allowing half-unit increments) and conjunctival redness evaluated by the Investigator at 7(± 1), 15(± 1), 20(± 1) minutes post-CAC (0-4 scale, allowing half-unit increments) at Visit 4b (duration of action visit) and 5a (onset of action visit).

Ocular itching will be evaluated by the subject using the following Ora Calibra® CAC Ocular Itching Scale:

Conjunctival redness will be evaluated by the investigator using the following Ora Calibra® Ocular Hyperemia Scale (half unit increments are allowed):

The average of each subject's eyes at each post-CAC time point will be used as the unit of analysis for both ocular itching and conjunctival redness.

The primary efficacy analyses for ocular itching and conjunctival redness will be conducted on the ITT population with LOCF for missing data using analysis of covariance (ANCOVA) models. These statistical models will include treatment group (including all four treatments: PRT-2761 0.5%, PRT-2761 1%, Vehicle, Patanol®) and the time point specific post-CAC scores at Visit 3 as a measure of baseline. Least square (LS) means for each treatment, the estimated treatment differences and their corresponding 95% CI, and p-values will be calculated from these ANCOVA models and will be used to compare each concentration of PRT-2761 and Patanol® to Vehicle and each concentration of PRT-2761 to Patanol®.

[REDACTED]
[REDACTED]
[REDACTED]
[REDACTED]
[REDACTED]
[REDACTED]
[REDACTED]

To demonstrate efficacy for ocular itching, PRT-2761 in any concentration needs to show clinical superiority over vehicle by [REDACTED] post-CAC time points, 5(± 1), 7(± 1), 10(± 1) minutes post-CAC and at least 1 unit for the majority [REDACTED] of the post-CAC time points. The same criteria will be used to demonstrate efficacy for conjunctival redness.

If ocular itching meets the efficacy measures as defined above with statistical significance ([REDACTED]
[REDACTED]

[REDACTED] the study will be considered a success for ocular itching. Similarly, if conjunctival redness meets the efficacy measures as defined above with statistical significance, then the study will be considered a success for conjunctival redness.

If both ocular itching and conjunctival redness meet the efficacy measures as defined above with statistical significance, then the study will be considered a success for both ocular itching and conjunctival redness.

Two-sample t-tests and non-parametric Wilcoxon rank sum tests will be used as unadjusted sensitivity analyses at each post-CAC time point. At each post-CAC time point, treatment differences will be considered statistically significant for each primary endpoint if they are significant at a two-sided significance level of $\alpha = 0.05$.

Sensitivity or supportive analyses will be performed on the following:

- ITT population with multiple imputation using MCMC methods for missing data;
- ITT population with BOCF for missing data;
- ITT population with observed data only;
- PP population with observed data only.

The number of subjects with itching scores less than one and with itching scores equal to zero will be summarized with counts and percentages by treatment group for each post-CAC time point at Visits 4b, 5a, 5b, 6a, 6b, and 7. For Visits 4b and 5a (acute phase), the number of subjects in each concentration of PRT-2761 and Patanol® will be compared to Vehicle and the number of subjects in each concentration of PRT-2761 will be compared to Patanol®. For Visits 5b, 6a, 6b, and 7 (chronic phase), the number of

subjects in each concentration of PRT-2761 and Patanol® will be compared to Pred forte® in addition to the treatment comparisons being made for the acute phase. A Fisher's exact test will be used to compare treatments for the number of subjects in each category and the corresponding p-values will be reported. Conjunctival redness scores will be summarized in a similar manner using categories of scores less than or equal to one and scores equal to zero.

Figures will be produced to show mean ocular itching score for each treatment arm by time point and visit (Visits 4b and 5a) for the ITT and PP populations with observed data only. Mean change from baseline of ocular itching scores for each treatment arm will be presented in a similar figure for the ITT population with observed data only. Mean conjunctival redness scores and mean change from baseline of conjunctival redness scores will also be presented in similar figures.

Separate listings of ocular itching scores and conjunctival redness scores for all subjects will also be provided.

13.2 Secondary Analyses

Secondary endpoints include ocular itching; conjunctival, episcleral, and ciliary redness; chemosis; tearing/watery eyes; eyelid swelling; rhinorrhea; nasal pruritus; ear or palate pruritus; and nasal congestion. All secondary endpoints will be analyzed in a manner similar to the primary endpoints for the ITT population with observed data only and for the PP population with observed data only. The ANCOVA models used will include treatment group (including all five treatments: PRT-2761 0.5%, PRT-2761 1%, vehicle, Patanol®/Patanol®, Patanol®/Pred forte®) and the time point specific post-CAC scores at Visit 3 as a measure of baseline. For the acute phase (Part 1), LS means for each treatment, the estimated treatment differences and their corresponding 95% confidence intervals, and p-values will be used to compare each concentration of PRT-2761 and Patanol® to vehicle and each concentration of PRT-2761 to Patanol®. For the chronic phase (Part 2), LS means for each treatment, and the estimated treatment difference and their corresponding 95% confidence intervals, and p-values will be used to compare each concentration of PRT-2761, Patanol®/Patanol® and Patanol®/Pred forte® to vehicle. Each concentration of PRT-2761 will also be compared to Patanol®/Patanol® and Patanol®/Pred forte® separately.

In addition, repeated measures ANCOVA models will be run for each visit, with treatment, time point, and time appropriate baseline as covariates. These models account for correlations between time points within each subject. LS means for each treatment, the estimated treatment differences and their corresponding 95% confidence intervals (as described previously for each phase) will be calculated from these repeated measures ANCOVA models. SAS code to implement this repeated measures ANCOVA model for each visit is as follows:

The Kenward-Roger method will be used to determine denominator degrees of freedom. An unstructured variance-covariance matrix will be used for the above repeated measures model. If the model does not converge using the unstructured matrix, the first order autoregressive structure and the compound symmetry structure will be employed, in that order.

The secondary analysis variables will be presented in subject listings by visit and time point as appropriate.

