
Visit 4b (Visit 4a+ 8 hrs [+1], Duration of Action Visit; CAC#1): CAC is performed 8 hours post Visit 4a dose, with post-CAC assessments of allergic signs and symptoms. Confocal will be performed on the same subset of subjects post all CAC assessments. This subset of individuals will also undergo tear collection prior to confocal.
 
Visit 5a (Day 15[±3] days), Onset of Action Visit; 2nd Dose/ CAC #2): In-office dose instillation with PRT-2761, PV or Patanol®. CAC is performed 15(+1) minutes post dose, with post-CAC assessments of allergic signs and symptoms.
 
Part 2: Chronic Allergic Conjunctivitis
 
Visit 5b (Visit 5a + 8 hrs [+1]; 3rd Dose/CAC #3)*: In-office dose instillation with PRT-2761, PV, Patanol®, or Pred forte® 8 hours from Visit 5a dose. CAC is performed 15(+1) minutes post dose, with post-CAC assessments of allergic signs and symptoms. The confocal subset of subjects will be dispensed cameras (Ora photography system) for at home assessments. All subjects will be dispensed diaries for at home assessments of allergy.
 
Visit 6a (Visit 5a + 24 hrs (±6 hrs) ; 4th Dose/CAC #4): In-office dose instillation with PRT-2761, PV, Patanol®, or Pred forte®. CAC is performed 15(+1) minutes post dose, with post-CAC assessments of allergic signs and symptoms.
 
Visit 6b (Visit 6a + 8 hrs [+1]; 5th Dose/CAC #5): In-office dose instillation with PRT-2761, PV, Patanol®, or Pred forte® 8 hours from Visit 6a dose. CAC is performed 15(+1) minutes post dose, with post-CAC assessments of allergic signs and symptoms. The confocal subset of subjects will also be dispensed cameras (Ora photography system) for at home assessments. All subjects will be dispensed diaries for at home assessments of allergy.
 
Visit 7 (6a + 24 hrs (±6 hrs) ; 6th Dose/CAC #6): In-office dose instillation with PRT-2761, PV, Patanol® or Pred forte®. CAC is performed 15(+1) minutes post dose, with post-CAC assessments of allergic signs and symptoms. Post all CAC assessments, the subset of subjects will undergo confocal microscopy and tear collection 2 hours (+1 hours) after instillation of the anesthetic used for confocal microscopy. Exit visit.
 
*15 of the subjects who were randomized to receive Patanol® at Visit 4a will continue to receive Patanol® at Visits 5a-7. The other 15 subjects who were randomized to receive Patanol® at Visit 4a will receive Patanol® at Visits 4a-5a and Pred forte® at Visits 5b-7.

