9 STUDY MATERIALS

9.1 STUDY TREATMENT(S)

9.1.1 Study Treatment(s)/ Formulation(s)/ Medical Device Composition or Design

PRT-2761 will be assessed in two concentrations as an ophthalmic solution:

- Concentration 1: PRT-2761 0.5%, n = 30
- Concentration 2: PRT-2761 1%, n = 30

The following will be the Reference Therapy:

- PV (vehicle), n = 30
- Patanol® (active), n = 15
- Patanol® during acute phase/Pred forte® during chronic phase (active), n = 15

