12.11 PRIMARY EFFICACY ANALYSES

The primary efficacy endpoints are ocular itching assessed at 5(± 1), 7(± 1), 10(± 1) minutes post-CAC (0-4 scale, allowing half-unit increments) and conjunctival redness evaluated by the Investigator at 7(± 1), 15(± 1), 20(± 1) minutes post-CAC (0-4 scale, allowing half-unit increments) at Visit 4b (Duration of Action Visit) and 5a (Onset of Action Visit). The average of each subject's eyes at each post-CAC time point will be used as the unit of analysis for both ocular itching and conjunctival redness. Ocular itching and conjunctival redness will each be analyzed using an analysis of covariance (ANCOVA) model for each post-CAC time point at each visit, with the time appropriate post-CAC scores at Visit 3 as a covariate and treatment group (including all four treatments: PRT-2761 0.5%, PRT-2761 1%, PV, Patanol®), as the sole factor. Least square (LS) means will be used to compare each concentration of PRT-2761 to PV. Two-sample t-tests will be used as unadjusted sensitivity analyses at each post-CAC time point, as well as a non-parametric Wilcoxon rank sum tests (comparing each concentration of PRT-2761 to PV). At each post-CAC time point, treatment differences

Treatment success is defined as PRT-2761, for at least one concentration, showing clinical superiority over PV [REDACTED]
[REDACTED] 5(± 1), 7(± 1), 10(± 1) minutes post-CAC for ocular itching and 7(± 1), 15(± 1), 20(± 1) minutes post-CAC for conjunctival redness, a [REDACTED]
[REDACTED] of the post-CAC time points measured for both ocular itching and conjunctival redness.

The primary efficacy analyses will be conducted on the ITT population using the last observation carried forward method for missing data as described in [Section 12.4](#).
Sensitivity or supportive analyses will be performed on the ITT population using observed data only, [REDACTED]
[REDACTED]
[REDACTED]

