12.12 SECONDARY EFFICACY ANALYSIS

Analyses will be performed on quantitative secondary endpoints in a manner similar to primary endpoints. Qualitative measures will be analyzed using Fisher's exact test or Chi-Square test as appropriate (comparing PRT-2761 to PV). Secondary endpoints include ocular itching (at Visits 5b, 6a, 6b, 7), conjunctival redness (at Visits 5b, 6a, 6b, 7), episcleral and ciliary redness, chemosis, eyelid swelling, tearing/watery eyes, rhinorrhea, nasal pruritus, ear or palate pruritus, nasal congestion (at Visits (4b, 5a, 5b, 6a, 6b, 7). The secondary endpoints will be analyzed for the ITT population with observed data only and for the PP population with observed data only. The exploratory measure, conjunctival inflammation, at Visits 3, 4b, and 7, will be analyzed as described above.

[REDACTED]
[REDACTED]
[REDACTED]
[REDACTED]
[REDACTED]

Additionally, similar analyses will be completed on all efficacy endpoints secondarily to compare each concentration of PRT-2761 to Patanol® [acute and chronic phase] and Pred forte® [chronic phase].

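### Does the five-level treatment factor in SAP 13.2 leave the acute-phase comparisons with Patanol undefined?

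*SAP*

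**What the plan says.** SAP 13.2 gives one description of the ANCOVA for the secondary endpoints: "The ANCOVA models used will include treatment group (including all five treatments", and the list that follows has PRT-2761 0.5%, PRT-2761 1%, vehicle, Patanol/Patanol and Patanol/Pred forte. No visit or phase restricts it.

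For Part 1 the section asks for LS means, differences, confidence intervals and p-values "to compare each concentration of PRT-2761 and Patanol® to vehicle and each concentration of PRT-2761 to Patanol". For Part 2 it names the two Patanol sequences and compares with each separately. The repeated-measures models take their comparisons from the same text: "as described previously for each phase) will be calculated from these repeated measures ANCOVA models".

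The primary ANCOVA at Visits 4b and 5a is different. SAP 13.1 says "These statistical models will include treatment group (including all four treatments", and Protocol 12.11 matches it: "treatment group (including all four treatments: PRT-2761 0.5%, PRT-2761 1%, PV, Patanol". Protocol 12.12 plans analyses "to compare each concentration of PRT-2761 to Patanol® [acute and chronic phase] and Pred forte® [chronic phase".

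The two Patanol sub-groups receive the same drug through Visit 5a. The footnote to the visit schedule in the Protocol Synopsis says that the switching group "will receive Patanol® at Visits 4a-5a and Pred forte® at Visits 5b-7". Protocol 9.1.1 gives that group's size: "Patanol® during acute phase/Pred forte® during chronic phase (active), n = 15".

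**The concern.** Nine secondary endpoints are analysed at Visits 4b and 5a: episcleral redness, ciliary redness, chemosis, tearing, eyelid swelling, rhinorrhea, nasal pruritus, ear or palate pruritus, and nasal congestion. At those visits a five-level factor splits one treatment according to a drug that will be given only later. The comparator named for Part 1 is not a level of that factor. Nothing visible in SAP 13.2 says whether the factor drops to four levels or the two Patanol levels are averaged.

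A programmer who requested default pairwise differences of LS means would get two answers for acute Patanol, each on half the arm, and the two could fall on opposite sides of 0.05. The pattern repeats over 9 endpoints × 2 visits × 3 time points = 54 ANCOVAs. Each has three Patanol comparisons (two concentrations and vehicle), so 54 × 3 = 162 per analysis population.

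**Working it through.** **Arm sizes.** Protocol 7.1 plans 120 enrolled subjects. The 1:1:1:1 allocation gives 120/4 = 30 per acute arm, and the 1:1 split of the Patanol arm gives 30/2 = 15 per sequence. The total is 3 × 30 + 2 × 15 = 120, which agrees with Protocol 9.1.1.

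**Precision of one Patanol comparison at Visits 4b and 5a.** The unit is the residual SD, the level is two-sided 0.05 (SAP 8.4), and there is one baseline covariate. The covariate's small contribution to the standard error is ignored. Residual df = N − number of levels − 1.

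| Route | SE | df | t | 95% half-width |
|---|---|---|---|---|
| Four levels, Patanol pooled | √(1/30 + 1/30) = 0.2582 | 115 | 1.9808 | 0.5114 |
| Five levels, two Patanol levels averaged | √(1/30 + ¼(1/15 + 1/15)) = 0.2582 | 114 | 1.9810 | 0.5115 |
| Five levels, one sequence alone | √(1/30 + 1/15) = 0.3162 | 114 | 1.9810 | 0.6264 |

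The second route is 0.5115/0.5114 = 1.0001 times the first, a loss of about 0.01%. The third is 0.6264/0.5114 = 1.22 times the first.

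**At the planned 112 completers**, assuming 28 per arm and 14 per sequence, the half-widths are 0.5298 (df 107), 0.5299 (df 106) and 0.6490 (df 106). The pattern is the same.

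**If the sub-groups are unequal.** Suppose 14 and 16 instead of 15 and 15 (an assumption). The averaged contrast then has SE √(1/30 + ¼(1/14 + 1/16)) = 0.2585, about 0.1% above 0.2582. Pooled and averaged estimates are then not identical, but their precision is still practically the same.

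**PRT-2761 against vehicle.** Both arms have 30 subjects under either factor. Only one residual df changes, so the half-width is 0.5114 or 0.5115.

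**Which route delivers what is asked.** For Part 1, SAP 13.2 requests one Patanol comparison. The first two routes supply it. The third supplies two comparisons that the acute-phase sentence does not name, and omits the one that it does. The acute-phase responder comparisons in SAP 13.1 also use a single Patanol group.

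**The case for a change.** The best case for a change is that the specific sentence should govern. SAP 13.2 opens by saying that secondary endpoints follow the primary approach, but it then sets five levels explicitly, and a specific statement normally displaces a general one. The analyst cannot simply fall back on the protocol, because SAP 1 says that the SAP's methods supersede it. SAP 18 declares no changes from the protocol-stated analyses, yet five levels at the acute visits would be one if taken literally. If one sequence alone were used, the cost would be real: at an assumed difference of 0.75 SD, power is 66% against 83% with the arm pooled. A clarifying sentence would cost almost nothing.

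What stands is that the coding for Visits 4b and 5a is not spelled out in the visible text, and that the five-level sentence is worded more broadly than it needs to be. The harm does not stand. The factor sentence says which levels enter the model; the next sentence says which comparisons come out of it, and for the acute phase that is one Patanol group. A five-level model with an averaged contrast satisfies both sentences literally.

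It is also not certain that the coding is unstated. The SAS code announced in SAP 13.2 is not visible, and lines are redacted directly after the comparison sentence in SAP 13.1 and before the Patanol comparison sentence in Protocol 12.12. Any of these may settle it.

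**Conclusion.** No change is needed. SAP 13.2 leaves a point of coding unstated, and its own acute-phase comparison sentence tells the analyst what result to produce. The two ways of producing it differ by about 0.01% in interval width at the planned arm sizes. The 22% figure should not be read as the expected effect, because it needs a reading that fails to give the requested comparison.

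The reach is limited to acute-phase secondary comparisons that involve Patanol. The primary ANCOVA already has four levels, the success criteria concern PRT-2761 against vehicle, and secondary PRT-2761 versus vehicle contrasts lose one residual df.

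This rests on the planned 30/30/30/15/15 allocation, roughly equal Patanol sub-groups at analysis and a common residual variance. Confidence that the coding is nowhere stated is only moderate, because relevant text is redacted or not visible.
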